1.0 BACKGROUND AND HYPOTHESES

1.1 The vast majority of caries observed in children ages 5 to 10 are on interproximal surfaces^{1,2}. Carious lesions on these surfaces are challenging to control and arrest due to difficulty reaching the contact area (in between teeth), limited salivary access, and poor flossing compliance in children and adolescents when flossing themselves³. Currently, for initial non-cavitated, demineralized lesions in these high caries risk patients, the standard of care has been to: reinforce oral hygiene instruction, advise in reducing the frequency of fermentable carbohydrate consumption, observe the incipient lesion at recall visits via bitewing radiographs every 6 months, and promote remineralization of the carious lesion with inoffice application of topical fluoride (i.e. 5% sodium fluoride varnish) over all teeth^{4,5}. Depending on the patient and the circumstances of their oral health condition, the practitioner may consider treating these lesions with restorations but a conservative, preventive approach is usually the initial goal of treatment.

Silver diamine fluoride (SDF) has been used for many years internationally, but in August 2014, SDF was cleared by the FDA as a medical device to treat dental hypersensitivity.⁶ More recently, the FDA granted SDF "Breakthrough Therapy Designation" on October 30, 2016 for caries arrest in children and adults in the United States under the product: Advantage Arrest Silver Diamine Fluoride 38% by Elevate Oral Care.⁶ The current formulation of 38% SDF is 25% silver for its antimicrobial effects, 5% fluoride for remineralization, and 8% ammonia to keep the silver and fluoride in solution.^{6,7} It has been touted as a very safe^{6,7} and possible noninvasive alternative and/or adjunct to topical fluoride treatment or restorative treatment.⁶ SDF has been shown to remineralize demineralized enamel or dentin, inhibit collagenases to protect dentin collagen from destruction, and have bactericidal properties to cariogenic bacteria including streptococcus mutans.^{7,8} Additionally, after the silver ions have killed the bacteria, they may be re-activated to do so again against subsequent or neighboring bacteria in a "zombie effect" to prevent incidence of new caries as explained by Horst et al.⁷ The silver and fluoride ions can penetrate up to 25 microns into enamel⁹ and 50-200 microns in dentin¹⁰, and promote remineralization while decreasing the depth of lesion.¹¹ Repeat applications, with a biannual maintenance regimen, have shown to arrest caries over time⁶.

2

Version date: 07/31/22

Most of the existing protocols for SDF application include direct microbrush topical application to the exposed carious lesion. However, with interproximal caries, microbrush application is difficult due to the unexposed broad contact area. The decision to treat initial interproximal lesions in children can be difficult when weighing patient behavior, extent of treatment and prognosis considerations. While there are other methods to treat interproximal caries such as resin infiltration, Mattos-Silveira et al. reports that there was a significant difference in children's discomfort when comparing resin infiltration to flossing or SDF application to initial interproximal caries lesions.¹² Currently, there is another study by Mattos-Silveira et al. in progress in Brazil that looks at the application of SDF in arresting interproximal carious lesions.¹³ This study uses a lower concentration (30%) than the current product used in the United States. Based on another study (Mei, ML et.al.) the 38% concentration of SDF appears to have a greater inhibition of metalloproteinases when compared to the 30% SDF and potentially this could lead to a greater arresting effect¹⁴.

Elevate Oral Care¹⁵ and others¹⁶ have suggested applying SDF to interproximal caries with the use of a woven or spongy floss, such as Oral-B Super Floss®. Like typical floss, Super Floss is made of nylon, but the non-waxed fibers have an interlocking network which gives it its spongy texture. Its sponginess is presumed to be more absorbent, allowing for easier delivery and application of SDF to interproximal carious lesions due to limited access with a microbrush. In 1981, Tsutsumi showed a significant reduction in the progress of existing caries and significant reduction in incidence of new caries in human primary molars when comparing flossing with plain unwaxed floss to SDF applied with unwaxed floss¹⁷. Therefore, Super Floss should be considered as a method for SDF delivery to interproximal lesions, but there is currently no information as to the efficacy of this treatment modality. **The purpose of this study is to investigate whether 1) SDF application using Super Floss can halt the progression/arrest and/or reverse/remineralize the initial interproximal caries and 2) whether SDF applied with Super Floss is more effective in arresting or remineralizing incipient lesion in comparison to:**

- a) SDF applied without Super Floss or
- b) Fluoride varnish applied alone

1.2 We hypothesize that:

- 1.21 SDF applied with Super Floss can reliably arrest and/or remineralize initial interproximal lesions.
- 1.22 SDF applied with Super Floss will be more effective than SDF applied without Super Floss or fluoride varnish applied alone in arresting initial interproximal caries.

2.0 OBJECTIVES AND PURPOSE

- 2.1 The primary aim of this prospective study is to test if 38% SDF application using Super Floss can reliably arrest caries in superficial interproximal lesions as determined by comparing time lapse bitewing radiographs.
- 2.2 The secondary aim is to test if SDF applied with Super Floss will be more effective than SDF applied without Super Floss or fluoride varnish applied alone in arresting initial interproximal caries also as determined by comparing time lapse bitewing radiographs.

3.0 STUDY DESIGN

- 3.1 Caries criteria is defined into 5 groups based on the zone of radiolucency using the International Caries Classification and Management System (ICCMS)¹⁸. This classification will be used by the present study to describe whether carious lesions have progressed based on comparing radiographs taken over time¹⁹ and allow for statistical analysis. The positioning of these bitewing radiographs must be consistent in showing the contact area and preventing overlap in the proximal teeth in question. ICCMS Classification is described as follows (Appendix I):
 - i. 0: No radiolucency/no caries not included in study
 - ii. RA: Initial Stages These are the target interproximal lesions for the present study
 - 1: Radiolucency in the outer half of enamel,
 - 2-Dentin-enamel Junction (DEJ): lesions extending within the inner half of enamel but not to DEJ,
 - 2+DEJ: lesions extending within the inner half of enamel including the DEJ,
 - 3: lesions extending to the outer one-third of dentin past the DEJ, and

- iii. RB: Moderate Stages and beyond These lesions will not included in present study because it is currently the standard of care to provide appropriate dental restorative treatment to repair the caries.
- 3.2 Each child with interproximal lesions on deciduous molar teeth meeting eligibility criteria RA Category 1, 2, or 3 will be invited to participate. Those who agree to participate will be randomly allocated to one of three treatments: Fluoride varnish (Control) application alone versus SDF application without Super Floss (Control) versus SDF application with Super Floss (Intervention). Daily flossing and oral hygiene instruction will be taught to patients of all study groups. Inclusion, Exclusion, and Withdrawal criteria are below in Section 5.
- 3.3 Follow-Up: Recall examinations and treatment reapplication will be done at 3 months, 6 months, and 12 months after the initial visit in accordance with current American Academy of Pediatric Dentistry (AAPD) guidelines for high caries risks patients⁵. Bitewing radiographs will be taken at 6 months and 12 months. This is in accordance with the "Prescribing Dental Radiographs..." guidelines as approved by the AAPD²⁰, which state that bitewing radiographs in high risk children with dental caries are recommended every 6-12 months.
- 3.4 Providers: Residents and Attendings at the Ostrow School of Dentistry at USC, Pediatric Residency Program. All residents and attendings participating in this study will be trained and standardized on how to identify lesions of interest on radiographs, obtain consent, and apply the medications.
- 3.5 Tracking of study participants: We will count the number of participants who:
 - 1. Those who are asked to participate
 - 2. Those who consent
 - 3. Those who drop out before randomization/after randomization
 - 4. Those who withdraw by their own choice for various reasons
 - 5. Those who are lost to follow up

Note: We will only collect and store clinical data for those participants who continue throughout the duration of the project. If a participant decides to drop out of the study at any time, then we will no longer collect data from the medical record during their ongoing clinical care. We will also discard any previous data we have collected on the participants that drop out.

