13.0 STATISTICAL CONSIDERATIONS

- 13.1 The proposed pilot Phase III randomized controlled clinical trial aims to determine which of the following treatments is superior in arresting dental caries among patients presenting with interproximal caries scoring RA1 RA3 on the International Caries Classification and Management System (ICCMS): (1) Fluoride varnish (FV, current standard of care, control), (2) Super floss + SDF + FV, (3) SDF + FV. We hypothesize that group 2 will have the best outcomes, as measured by no change or reversal in ICCMS classification indicating no caries progression or remineralization on radiographic examination, (higher score indicates progression) followed by group 3. As we could find no data on ICCMS-defined progression or remineralization rates for either Super Floss or fluoride, we were unable to calculate power. Instead, we provide estimates of recruitment based on feasibility. We expect to accrue approximately 20 participants, with 2 qualifying teeth per participant, in each group.
- 10% loss to follow up has increased dramatically to ~48%. Given this unexpected setback, we now need to continue recruiting participants to reach sufficient power. We originally planned to enroll 39 subjects in the study, but would now like to add 21 new participants for a total of 60 participants.

Descriptive statistics will be calculated for all demographic and clinical characteristics to assess the degree to which randomization was successful using means and standard deviations or medians and interquartile ranges for continuous variables and counts and percentages for categorical variables.

The primary analysis will be by intent-to-treat. The primary outcome is the change in ICCMS category, as assessed by radiographic evidence, from baseline to 12 months, with a planned interim analysis to evaluate the endpoint at 6 months for early indications of efficacy. We will calculate the median difference at each time point and use an individual-level model with an adjustment to the standard error to account for the clustering. First we will evaluate the association between treatment groups and the change in ICCMS score from baseline at 6 and 12 months using a cluster-adjusted chi-squared test. We will further assess

14

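### Discarding the data of children who drop out contradicts the intent-to-treat analysis, and the only named missing-data method is switched off at the loss the plan reports

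*Combined protocol and SAP*

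**What the plan says.** Section 3.5 lists the groups to be counted. Item 3 is "Those who drop out before randomization/after randomization"; item 4 is withdrawal by choice; item 5 is "Those who are lost to follow up". The Note beneath opens with "We will only collect and store clinical data for those participants who continue throughout the duration of the project". It then says that collection stops when a participant decides to drop out, at whatever time, and ends with "We will also discard any previous data we have collected on the participants that drop out".

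Section 13.0 states "The primary analysis will be by intent-to-treat". The outcome is change in ICCMS category to 12 months, "with a planned interim analysis to evaluate the endpoint at 6 months for early indications of efficacy". On missing data, it will consider multiple imputation if less than 10% is missing, compare children with and without missing data on demographic and clinical variables, and, if imputation is used, repeat the analysis without the imputed children. No rule is given for 10% or more.

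The same section reports that "10% loss to follow up has increased dramatically to ~48" per cent. Its stated response is to recruit further, from 39 to 60 children.

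**The concern.** An intent-to-treat analysis keeps each randomised child in the assigned arm. A child whose record has been discarded cannot be kept there. The baseline and 6-month categories that might show whether drop-outs differ from the rest, or that might inform an imputation, are lost with the record, and deletion cannot be undone.

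The second problem is separate. At the reported loss, the plan's own condition rules out imputation and the sensitivity analysis tied to it. What remains is GEE on whatever records exist, a default that the plan neither states nor defends.

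Section 10.0 says that neither the treating dentist nor the family is blinded. Leaving the study could therefore depend on both the arm and how the lesion is doing. Recruiting more children improves precision but does nothing about selective loss.

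**Working it through.** **Part A: the discard rule against the analysis plan**

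- *Who is covered.* Item 3 of Section 3.5 includes drop-out after randomisation, and the Note sets no time limit. Randomised children are covered.
- *Intent-to-treat (Section 13.0).* It requires these children in their assigned arm. After deletion only a count remains.
- *Comparison of children with and without missing data (Section 13.0).* It needs demographic and clinical variables on the children with missing outcomes. Deleted children have none, so the comparison omits them.
- *Interim analysis at 6 months (Section 13.0).* A child included at 6 months who drops out at, say, 9 months must be deleted. The final data set then no longer reproduces the interim result.

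**Part B: the 10% condition against the reported loss**

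Inputs, all from Section 13.0: 39 children planned, 21 added; "We expect to accrue approximately 20 participants, with 2 qualifying teeth per participant, in each group"; loss about 48%; imputation considered only below 10% missing.

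1. Enrolment: 39 + 21 = 60, which agrees with 3 × 20 = 60.
2. If 48% applies to all 60 children, equally by arm: 60 × 0.48 = 28.8, about 29 without a 12-month outcome. Observed per arm: 20 × 0.52 = 10.4.
3. Ceiling for imputation: 60 × 0.10 = 6, so fewer than 6 children. Expected loss over ceiling: 28.8 / 6 = 4.8.
4. If instead 48% applies only to the 39 children first planned (39 × 0.48 = 18.7) and none of the 21 added children is lost: 18.7 / 60 = 31%. If the added children are lost at the earlier 10%: (18.7 + 2.1) / 60 = 35%.

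The condition fails on each of these readings.

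**Part C: how many records the discard rule removes**

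If active drop-outs are a fraction f of the 28.8 children lost, records discarded = 28.8 × f. The documents do not give f. Assumed values:

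| f (assumed) | children discarded |
|---|---|
| 0 | 0 |
| 10% | 2.9 |
| 25% | 7.2 |
| 50% | 14.4 |
| 100% | 28.8 |

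If the 48% means item 5 alone, drop-outs come on top of it and nothing in the plan gives their number.

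**The case against.** **Scope.** A reader might infer that about 48% of records will be destroyed. The documents do not support this. The discard sentence names drop-outs, the 48% is called loss to follow-up, and Section 3.5 counts the two separately. The Note's opening sentence could be read to reach everyone who does not continue to the end. Against that, Section 13's provision for missing outcomes suggests that some incomplete records are kept. The number discarded may be small.

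**Bias.** A reader might also infer a bias of a particular size. The plan gives no arrest rates, retention by arm or timing of loss from which to derive one. Any such figure would describe selective loss in general, most of which could arise even with every record kept, not the harm added by the discard rule. Different loss by arm is not enough for bias: GEE on available data remains valid when loss depends only on covariates in the model, including arm. The worry is loss related to outcome within arms, which unblinded treatment makes plausible but does not demonstrate.

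**Missing data.** Restricting imputation to small amounts of missing data can be defended as caution, and making it the primary analysis with about 10 observed children per arm would be contestable. That stands, and is why imputation is proposed below only as a sensitivity analysis. Section 13 does contain a safeguard in its comparison of children with and without missing data. It is descriptive, however: it does not show how the treatment comparison would change, and deleted children cannot enter it.

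**Tooth withdrawals.** A reader might extend the discard rule to teeth withdrawn under Section 5.3. The Note concerns participants, and no section says that outcomes of withdrawn teeth are discarded.

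**Consent.** The rule may reflect a promise to families. The consent pages are not available, so this cannot be settled here; it limits how the fix can be applied.

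None of this reconciles Section 3.5 with the intent-to-treat statement.

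**Conclusion.** The contradiction stands on the text alone: for any child who drops out after randomisation, the discard rule and the intent-to-treat analysis cannot both be carried out. The number of such children is unknown, and no bias can be attributed to the rule from the documents. It should be corrected while recruitment continues, because each deletion is permanent.

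The missing-data gap also stands and is the lesser of the two. About 29 of 60 children would lack a 12-month outcome if 48% applies throughout, and about 19 (31%) if it applies only to the first 39 with no later loss. Either way the stated condition excludes imputation and its linked sensitivity analysis, leaving an available-records analysis with nothing to show how far the result depends on selective loss. This assumes that the 48% counts children rather than teeth; the figure of about 10 observed per arm also assumes equal loss across arms.

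**What to change.** 1. **Section 3.5.** Replace the Note with: *Data collected up to withdrawal or loss to follow-up are retained and analysed in the assigned arm; collection stops at withdrawal.* Apply this subject to consent already given. Report by arm the number of any records already discarded.
2. **Section 13, primary analysis.** Define the primary set as all randomised children, with GEE on all available 6- and 12-month radiographs. Delete the 10% condition. Children with no follow-up radiograph add nothing to the GEE estimate but should be reported by arm and covered by the sensitivity analyses.
3. **Section 13, sensitivity analyses.** Add (a) multiple imputation using arm, baseline category and, where available, 6-month category, allowing for clustering within child; and (b) a range of assumptions for missing outcomes that differ by arm.

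**Cost.** IRB approval and modest extra analysis; no extra visits or participants. If enrolled families were told that their data would be discarded, the new rule may need re-consent or may apply only to later enrolments. With about 10 observed children per arm, the imputation model must be simple, and the sensitivity results will be wide and model-dependent. They will show how fragile the result is but will not restore the lost information.

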4.0 DRUG/DEVICE INFORMATION

- 4.1 Drug/Device Name
 - 4.1.1 Advantage Arrest 38% Silver Diamine Fluoride
 - 4.1.2 Voco ProFluorid Varnish
 - 4.1.3 Oral-B Super Floss
- 4.2 Manufacturer:
 - 4.2.1 Elevate Oral Care ([name])
 - 4.2.2 VOCO GmbH ([name])
 - 4.2.3 The Procter & Gamble Company ([name])
- 4.3 Chemical makeup, based on manufacturer's MSDS:
 - 4.3.1 SDF: Ag(NH3)2F. The silver is antibacterial, the fluoride aids in remineralization of the tooth, and the ammonia suspends the two in solution. One drop contains 25 μL and 9.5mg of SDF.

CAS #	Ingredient	Percentage (%)
7440-22-4	Silver (Ag)	24 - 27
1336-21-6	Ammonia (NH3)	7.5 - 11
16984-48-8	Fluoride (F)	5 - 6
3844-45-9	FD&C Blue #1	<1
7732-18-5	Deionized Water	≤62.5

4.3.2 Fluoride varnish: 5% NaF

CAS #	Ingr	redient Percentag	e (%)
64-17-5	Etl	hanol 10 - 2	25
7681-49-4	Sodium	n Fluoride 2.5 -	5

- 4.3.3 Super Floss: No hazardous ingredients as defined by OSHA and/or WHMIS.
- 4.4 Dose/Formulation:
 - 4.4.1 SDF: One drop contains 25 μ L and 9.5mg of SDF, which can be applied to ~5 lesions.
 - 4.4.2 Fluoride Varnish: 1 mL suspension contains 50 mg NaF, equivalent to 22.6 mg fluoride ion. 1 unit package = 0.4 mL, which is 20 mg NaF. Approximately 0.25mL is used for patients with primary dentition, and 0.40mL is used for adolescent patients or permanent dentition.

4.4.3 Super Floss: N/A

4.5 Toxicity or adverse effects,:

- 4.5.1 SDF: SDF is corrosive to metal and glass, and can be an eye, skin, mucosal, respiratory, and gastrointestinal irritant. Repeated overexposures may cause mottled teeth or fluorosis on teeth/bones (not in the dosage used in this study). In the UCSF Protocol by Horst et al. 2016, they found SDF to be extremely safe, citing not one adverse event in over 80 years of use in Japan and mild temporary side effects found in 3 of 1,493 subjects in 9 clinical trials. The lethal dose (LD50) of SDF, determined by female and male mouse and rat studies, was found to be: 520 mg/kg by oral administration, and 380 mg/kg by subcutaneous administration. Considering a small child weighing 10kg with caries, the dose would be 0.95mg/kg (One drop of SDF contains 9.5mg and one drop is usually adequate to treat one patient). For that 10kg child, the relative safety margin of using an entire drop would be: 380 mg/kg LD50 / 0.95 mg/kg dose = 400-fold safety margin.
- 4.5.2 Fluoride varnish:
 - Sodium Fluoride: Oral rat LD50: 52 mg/kg
 - Ethanol: Oral rat LD50: 7060 mg/kg

Fluoride varnish can be an irritant with direct eye contact and prolonged skin contact. If ingested, it may cause salivation, nausea, vomiting, abdominal pain, headaches, or dizziness. Repeated overexposures may cause fluorosis.

For a similar calculation above for a 10kg child, the relative safety margin of using an entire 0.4 mL unit (one package) of fluoride varnish would be: 52 mg/kg LD50 / 2.0 mg/kg = 26-fold safety margin.

- 4.5.3 Super Floss: There are no toxic or adverse effects listed, and there are no hazards when used as directed.
- 4.6 Non-medical Side Effects:
 - 4.6.1 SDF: SDF stains carious lesions. It also can have a bitter or metallic taste. It can also stain or darken skin with a 'temporary tattoo' which resolves in 2-14 days after normal skin exfoliation. SDF can also stain hard surfaces like table tops as well as clothing.⁷
 - 4.6.2 Fluoride Varnish: N/A
 - 4.6.3 Super Floss: N/A

- 4.7 Risk:
 - 4.7.1 SDF: Minimal
 - 4.7.2 Fluoride Varnish: Minimal
 - 4.7.3 Super Floss: N/A
- 4.8 Storage:
 - 4.8.1 SDF: Store in a cool dry place in provided closed container.
 - 4.8.2 Fluoride Varnish: Store in a cool, dry place in original sealed package away from direct sunlight.
 - 4.8.3 Super Floss: N/A
- 4.9 Stability, based on manufacturer's MSDS:
 - 4.9.1 SDF is a light sensitive liquid. Prolonged exposure to light or evaporation will cause precipitation.
 - 4.9.2 Fluoride varnish is a stable product.
 - 4.9.3 Super Floss: N/A

